This design allows us to test the overall effect of weight loss and the overall effect of sodium restriction. The effect of the combined intervention can also be tested. In addition, we will examine the effect of the combined intervention as compared to weight loss, sodium restriction and the absence of weight loss and sodium restriction.

All nine clinics will randomize participants into all four arms and subjects will be distributed equally among the three treatment groups and the control

group (1/4 each). Randomization will be stratified by clinic to insure even distributions into the four treatment groups at each of the clinical centers.

SAMPLE SIZE AND POWER

- A. The hypotheses to be tested in this factorial design are 1) the overall effect of weight loss (i.e., groups A and B vs. groups C and D); 2) the overall effect of sodium restriction (i.e., groups A and C vs. groups B and D); and 3) the effect of the combined intervention (i.e., group A vs. group D). The primary endpoint for testing these hypotheses will be change in mean diastolic blood pressure (DBP) both from baseline to termination BP and from baseline to the average of all DBP's from 6 months to 36 months. The assumptions for calculating the necessary sample size for these continuous endpoints are as follows:
 - 1. Baseline blood pressure measurements will be taken at 3 visits with three measurements per visit. Follow-up BP measurements will be taken over 3 visits at 18 and 36 months, and 1 visit at 6, 12, 24 and 30 months, each with 3 measurements per visit. The termination BP is defined as the BP at 36 months or before starting BP medication, which will also be based on 3 visits with 3 measurements per visit. The blood pressure measure for an individual is thus an average of nine readings at baseline and at termination. The variance of the change from baseline (x_1) to termination (x_2) can be written as:

$$\sigma_1^2 = V(x_2 - x_1) = 2\sigma_p^2(1 - \rho_{0,36}) + 2(\sigma_A^2 + \sigma_e^2/k)/n$$

where σ_{p}^{2} = between-person variance

 σ_{λ}^{2} = between-visit variance

 $\sigma_{\rm e}^2$ = within-visit variance

n = number of visits = 3

k = number of measurements per visit = 3

 $\rho_{\text{i,j}}$ = tracking correlation of the individual's true blood $pressure\ mean\ from\ time\ i\ to\ time\ j,\ with\ 0\ representing$ baseline

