Furthermore, at its meeting of September 16, 1992, the Data and Safety Monitoring Committee recommended that safety monitoring be performed for systolic blood pressure of 140-159 mmHg just as for diastolic blood pressure $_{\geq}90$ mmHg or systolic blood pressure $_{\geq}160$ mmHg. This followed the availability of a draft of the JNCV report which labeled systolic blood pressure of 140-159 mmHg as Stage I hypertension. The recommendation was approved by the Steering Committee on September 29, 1992.

Sample size calculations for having diastolic blood pressure $_{\geq}90$ mmHg or taking antihypertensive medication are presented first and are based on the following assumptions:

- 1. Power is computed using two estimates of the event rate (DBP $_{\geq}90$ or on hypertensive medication) over an average 3.5 years of follow-up:
 - a. The rate reported among the high weight controls in HPT (38) for the same endpoint is 30.2% over 3 years of follow-up. This was calculated as a proportion of all participants, and thus takes loss to follow-up into account. The data from Phase I of TOHP are consistent with this estimate. Among high weight controls with initial DBP's of 83-89 mmHg the incidence of hypertension by this definition is 12.5% in one year, or 33.0% extrapolating to 3 years. Extrapolating the HPT rate to 3.5 years yields an estimated event rate of 34.5% in the control group for this study.
 - b. The HPT data are based on a single visit, and may thus

overestimate the incidence of hypertension. An event rate of 29.7% was derived from the estimates of the one year event rate in TOHP Phase I and simulations using the gamma distribution with parameters based on NHANES II data (44) and the event rates in HPT (38). This assumes blood pressure measurements over 3 visits to determine the development of hypertension, as in the current study. A 10% loss to follow-up is assumed, reducing the event rate to 26.7% in the control group.

- 2. The expected reductions in the event rate are 30% for weight loss, 20% for sodium restriction, and 40% for weight loss plus sodium restriction. These expected reductions were based on the results of Phase I and other trials of primary prevention (HPT, PPH, and HIP). This assumes subadditivity of effects. Under the additive model the risk reduction in the combined intervention group would be 44%.
- 3. The sample size is estimated to be 2250 subjects as outlined above.

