 The number in each comparison group will be 1125 for the overall weight loss and sodium restriction hypotheses and 562 for the combined intervention versus control hypothesis.
- 4. A Bonferoni adjustment for three comparisons is made.
- 5. The power is calculated for the logrank test using the following formula (45):

Power =
$$\Phi$$
 [\sqrt{d} |1- θ / 1+ θ | - z_{α}] where
$$d = N(2 - p_{o} - p_{1})$$

$$\theta = \ln p_{o} / \ln p_{1}$$

and

N = number in each group

 \mathbf{p}_{\circ} = probability of remaining normotensive in the comparison group

 p_1 = probability of remaining normotensive in the active

group

 $z_{\alpha} = 2.394$

Estimates of power are given in Table 5. The relative risks listed in the table represent the average risk reductions for the main effects of the single interventions when using all four groups. Using these assumptions the power to determine the effectiveness of weight loss alone is at least 93.6% for this endpoint while that for sodium restriction is no more than 65.4%. The power is over 97% to detect the hypothesized difference between the combined intervention and control groups in development of hypertension. This study, however, has little power to detect differences between the combined intervention and either single intervention group with these expected reductions. The power to detect a difference between the combined and sodium restriction group is at most 62%, while that for the combined vs. weight loss group is 16%.

The revised primary categorical endpoint is the development of systolic or diastolic hypertension, defined as DBP $_{2}$ 90 mmHg, or SBP $_{2}$ 140 mmHg or taking antihypertensive medication. The HPT saw an incidence rate of 38.7% for this endpoint among high weight controls over 3 years. Extrapolating to 3.5 years leads to a rate of 43.5%. All other assumptions remain the same. The increase in monitoring for systolic blood pressure of 140-159 mmHg is likely to increase the incidence of this endpoint. Simulations were performed using a random effects model and the parameters given in sections A and B above and with the additional assumptions of population means of 128.4 mmHg for SBP and 82.0 mmHg for DBP, and a correlation of SBP and DBP of 0.80. An effect of adjustment to the study situation was also assumed (a lowering of mean BP in addition to the expected regression to the mean). These simulations suggest that the incidence of the combined endpoint may

TOHP II Protocol 12/15/92

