To assess the effects of weight loss, sodium restriction, and their combination, the mean changes in DBP at 36 months in the various groups will be compared. Additionally, the average of all BPs obtained during the trial in the various groups will be compared. The analysis of variance for a two-by-two factorial design will be used to test the main effects of weight loss and of sodium restriction. Multiple regression analyses will be performed to adjust for other covariates, such as age, sex, and initial weight and urinary sodium. To reduce the impact of regression to the mean and to improve the error variance, as well as to adjust for any imbalance, mean initial DBP will also be included in the model. To compare DBP changes in two of the four groups, such as the combined intervention versus placebo, comparisons of means

with a t-test and multiple regression analyses will similarly be used. These methods can also be used to explore the effect of the combined intervention compared to a single intervention such as weight loss alone. More sophisticated methods of longitudinal data analysis such as computing slopes over time or the use of autoregressive models will be used to explore more complex changes in DBP over time in the various treatment groups (48-50).

Because the effect of treatment may not be uniform across all members of a group, we will also examine the distribution of blood pressure changes. Should these appear not to be normally distributed, we will perform nonparametric tests of significance. To examine the effect of actual compliance to the treatment regimen, we will consider change in DBP as a function of actual change in weight and urinary sodium. This is of particular importance because some members of the control group may seek to implement the intervention strategies on their own.

Censoring of this continuous variable due to incidence of hypertension is a potential problem in this analysis. Once antihypertensive medications are prescribed, blood pressure readings become biased in those subjects who should have the highest levels. For this reason we will attempt to acquire and use termination blood pressures obtained prior to initiation of antihypertensive therapy. Furthermore, individuals who are told they are hypertensive may begin some nonmedical intervention; such as weight loss, on their own, perhaps under the advise of their physicians, even if they do not take medications.

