Several strategies may be used to deal with the effects of such biases. The primary analysis will use the termination blood pressure as defined in Phase I of TOHP. This is the last recorded blood pressure prior to the initiation of

drug therapy. This includes blood pressures measured after becoming an endpoint according to the definition of SBP $_{\geq}140$ mmHg or DBP $_{\geq}90$ mmHg, but prior to starting medication. Because it is recognized that these latter measurements may be biased, secondary analyses will be performed to confirm the results of the primary analysis. These include an analysis of blood pressures taken at the time of diagnosis for those who become hypertensive, imputing minimum values of 90 mmHg for DBP and 140 mmHg for SBP for those who go on BP medications, and also a multivariate repeated measures analysis. The latter approach would use all measured blood pressures on an individual either including or excluding those following diagnosis. In this way, both the within-person variation as well as an effect of "self-intervention" could be taken into account.

Secondary endpoints in the trial, including changes in SBP and the development of diastolic and systolic hypertension, will also be examined. The former will be evaluated in the same manner as changes in DBP described above. For the hypertension endpoints, crude relative risks and a chi-square test will be calculated for each hypothesis to compare cumulative incidence rates over the duration of the study. We will compute Kaplan-Meier incidence-free survival curves and the logrank test statistic. A Cox proportional hazards regression analysis will be performed to adjust for potential confounders such as baseline BP, age, sex, and race.

Intermediate variables such as urinary sodium and body weight will be monitored on a regular basis and compared across intervention groups.

This trial will also provide the opportunity to explore any differential response to intervention by race, and gender, as well as body mass index,

waist to hip ratio, cigarette smoking habits, pulse rate, family history of hypertension, and baseline electrolyte excretion. Currently we expect to recruit a sample with approximately 21% blacks and 33% women. While power will not be adequate to test the effect of the interventions within these subgroups, we will explore any differences among them.

STUDY ADMINISTRATION

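### Minor improvement: stratify the hypertension main-effect tests by the other randomised intervention, which gains 0.7 to 1.4 points of power for the sodium logrank test at almost no cost

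*Protocol*

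**What the plan says.** For DBP, DATA ANALYSES states: "The analysis of variance for a two-by-two factorial design will be used to test the main effects". Changes in SBP are to be handled in the same way. For the hypertension endpoints the same section turns to other methods: "crude relative risks and a chi-square test will be calculated for each hypothesis to compare cumulative incidence rates", then "We will compute Kaplan-Meier incidence-free survival curves and the logrank test statistic". A Cox model follows, adjusted for confounders for which baseline BP, age, sex and race are given as examples. The other randomised intervention is named in none of these hypertension analyses.

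SAMPLE SIZE AND POWER, part A, defines the sodium hypothesis as "the overall effect of sodium restriction (i.e., groups A and C vs. groups B and D". In part C the logrank power comes from a two-group formula: "The number in each comparison group will be 1125 for the overall weight loss and sodium restriction hypotheses". The effects in Table 5 "represent the average risk reductions for the main effects of the single interventions when using all four groups".

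**The concern.** A factorial trial gives each main-effect test a randomised, fully observed and balanced second factor. By the protocol's own assumptions that factor is prognostic: averaged over sodium assignment, weight loss cuts the hypertension rate by 28%. The DBP analysis uses this information. On their natural reading the hypertension tests do not, because they compare two pooled groups with two pooled groups. For time-to-event and binary outcomes, leaving out a prognostic factor costs a little power.

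The loss matters most for sodium restriction, the weaker of the two main effects. Its stated power is 65.4% and 48.0% for diastolic hypertension (Table 5), and 82.5% and 87.0% for the combined endpoint (Table 6). At stake is a small amount of power that could be recovered without new participants or new data.

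**Working it through.** **Inputs** (SAMPLE SIZE AND POWER, part C)
- "The expected reductions in the event rate are 30% for weight loss, 20% for sodium restriction, and 40% for weight loss plus sodium restriction".
- Control event rates: 26.7% and 34.5% (diastolic hypertension), 43.5% and 47.2% (combined endpoint).
- 1125 per side, so 562.5 per cell.
- "A Bonferoni adjustment for three comparisons is made", which gives z = 2.394.

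For a control rate r, the cell risks are r (usual care), 0.7r (weight loss), 0.8r (sodium) and 0.6r (combined). The pooled sodium comparison is (r + 0.7r)/2 = 0.85r against (0.8r + 0.6r)/2 = 0.70r. The average reduction is 1 − 0.70/0.85 = 18%, as in the tables.

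**Step 1: reproduce the protocol's sodium power.** Its formula is Power = Φ[√d · |(1−θ)/(1+θ)| − 2.394], with d = N(2 − p₀ − p₁) and θ = ln p₀/ln p₁. At r = 43.5%:
- p₀ = 1 − 0.36975 = 0.63025 and p₁ = 1 − 0.3045 = 0.6955
- d = 1125 × 0.67425 = 758.5 and θ = 1.271
- √758.5 × 0.271/2.271 = 3.29, so Power = Φ(3.29 − 2.394) = 81.5%, against 82.5% stated

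The other three rates give 48.1% (stated 48.0%), 65.0% (65.4%) and 86.7% (87.0%). The stated powers therefore follow, within about 1 point, from rates collapsed over weight-loss assignment.

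**Step 2: collapsed against stratified logrank.** Event times are taken as exponential in each cell. With R₀, R₁ the expected numbers at risk and d₀, d₁ the expected event intensities on the two sides:
- U = Σ ∫ [d₀ − (d₀+d₁) R₀/(R₀+R₁)] dt
- V = Σ ∫ (d₀+d₁) R₀R₁/(R₀+R₁)² dt
- z = U/√V and Power = Φ(z − 2.394)

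The sum runs over one stratum (collapsed) or over two (without and with weight loss).

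| Control rate | z collapsed | z stratified | Power collapsed | Power stratified | Gain (points) | Squared z ratio |
|---|---|---|---|---|---|---|
| 26.7% | 2.351 | 2.369 | 48.3% | 49.0% | 0.7 | 1.015 |
| 34.5% | 2.787 | 2.818 | 65.3% | 66.4% | 1.1 | 1.022 |
| 43.5% | 3.303 | 3.356 | 81.8% | 83.2% | 1.4 | 1.032 |
| 47.2% | 3.526 | 3.591 | 87.1% | 88.4% | 1.3 | 1.037 |

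The squared z ratio is the equivalent increase in sample size: 1.5 to 3.7%, or about 34 (0.015 × 2250) to 83 (0.037 × 2250) participants.

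**Step 3: check by simulation.** In 20,000 simulated trials per rate, with 562 per cell, sodium power rose from 65.3 to 66.3% at r = 34.5%, 82.0 to 83.1% at 43.5%, and 87.5 to 88.6% at 47.2%. The gains are 1.0, 1.1 and 1.1 points.

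**Step 4: chi-square.** Crude test against Mantel-Haenszel over weight-loss assignment, two-sided alpha 0.05/3:
- 26.7%: 48.0 to 48.4%
- 34.5%: 64.8 to 65.3%
- 43.5%: 81.1 to 81.7%
- 47.2%: 86.3 to 86.9%

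The gain is 0.3 to 0.6 points, about half that of the logrank test or less.

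**Step 5: weight loss.** Stratifying the weight-loss logrank by sodium assignment gains at most 0.13 points, because the omitted sodium effect is smaller and power is already 93% or more.

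**Step 6: what a stratified summary averages.** The assumed reductions are subadditive. Sodium lowers risk by 20% without weight loss, but by 1 − 0.6/0.7 = 14% with it. At r = 43.5% the stratum hazard ratios are ln(0.652)/ln(0.565) = 0.75 and ln(0.739)/ln(0.6955) = 0.83.

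**The case against.** Four points can be made against this.

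- **The logrank collapse is not stated.** Only the chi-square sits beside the word crude. The logrank is left unqualified, the Cox list is open-ended, and strata are often left to an analysis plan, which is not at hand. The two-group power formula is also weak evidence. Table 1's 69.5% at 1.0 mmHg comes from the same kind of formula (1125 × 0.689 = 775 per side, SD 6.78, 1.0/(6.78 × √(2/775)) = 2.90, Φ(2.90 − 2.394) = 69.5%), yet DBP is analysed factorially. This stands. Collapsing is the natural reading, not a declared one.
- **Nothing is invalid.** A reader might infer a type I error problem. The documents do not support that: with one quarter of participants in each randomised group, the collapsed tests keep their level. Nor is the collapsed hazard ratio biased. It estimates the pooled contrast that the protocol defines.
- **The size is small.** A reader might apply a gain of more than 1 point to every main-effect test. It reaches that only for the sodium logrank at the three higher event rates. It is also well below the 17.4 points between the two sodium columns of Table 5 (65.4% and 48.0%).
- **The endpoint is secondary.** Hypertension is listed among the secondary endpoints, although the combined definition is called the primary categorical one. The DBP analysis is unaffected.

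All four limit the weight of the point. None argues against a change that is nearly free and tests the same main effect.

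**Conclusion.** This is a minor efficiency and consistency improvement, not an error. As written, the hypertension main-effect tests most naturally collapse over the other randomised factor, while the DBP tests do not. The collapsed tests are valid, and no design conclusion changes. The largest benefit is 1.4 points, for the sodium logrank test.

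The figures assume exponential event times, hence proportional hazards within each weight-loss stratum, equal cells, the protocol's assumed reductions, and no loss to follow-up beyond what its event rates already contain. The design figure that labels groups A to D is not reproduced. That A is combined, B weight loss, C sodium and D control follows from how the three hypotheses are defined.

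**What to change.** Add to the hypertension paragraph of DATA ANALYSES: *The main effect of each intervention on hypertension will be tested by a logrank test stratified by assignment to the other intervention, with a Mantel-Haenszel test for cumulative incidence. The Cox model for the main effects will include indicators for both interventions. Stratum-specific estimates will be shown alongside.* Keep the plain two-group test for combined versus usual care.

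The cost is a sentence or two of wording, with no new data and two large strata per test. There is one small downside: under the assumed subadditivity, a stratified hazard ratio averages effects that differ between strata. That is why the stratum-specific estimates should be reported with it.

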GROUP GOAL	≥ 10 lb weight loss 6 months post randomization and maintained throughout	24 hour urinary Na+ excretion ≤ 80 mEq (1800 mg) by 6 months post-randomization and maintained throughout	(a) + (b)
PARTICIPANT OBJECTIVE	Weight loss ≥ 10 lb or achievement of ideal weight; evidence of caloric restriction and increased physical activity in self-reports	Decrease in dietary Na+ intake to 1600 mg by six month estimated from dietary self- reports and urinary excretion data	(a) + (b)
CONTENT	-Information about weight control -Directed group process -Behavioral counseling -Food experience -Social support for adherence -Experiences in moderate physical activity	-Information about Na+ -and all other items on (a)	(a) + (b)
CONTACT SCHEDULE	Intensive: 1 individual, 14 weekly sessions, 6 biweekly sessions Extended: biweekly contacts with monthly face-to-face meetings until the intensive intervention is completed for the first cohort then mini-modules to be offered with continued bi-weekly contact Specially tailored follow-up where indicated	Intensive: 1 individual, 10 weekly sessions, 4 monthly sessions *Extended: monthly contacts with bi-monthly meetings until intensive intervention completed for the first cohort then mini-modules offered with a min. of quarterly overnight urine collections with a face- to-face contact. Specially tailored follow-up where indicated.	Same as (a)
CONTACT MODE	Primarily group; individual contacts at post-randomization, and as needed thereafter	Same	Same
ADHERENCE FEEDBACK	-Attendance records -Weigh-ins -Food records -Physical activity records	-Attendance records -Food records -Overnight urine Na+ or other urine monitoring methods	(a) + (b)
SAFETY ISSUES	-Diet quality -Physical activity- related injuries -Weight cycling	excessive sodium restriction	(a) + (b)
